11.3.2 Sleep Disturbance by Visit

For the sleep disturbance as assessed by the CSDI, the total CSDI score after 3 weeks of double blind treatment and during open-label treatment will be analysed as for TST.

11.3.3 CGAS by Visit

The CGAS score after 3 weeks of double blind treatment and 13 weeks of open-label treatment will be analysed as detailed above for TST.

11.3.4 SDQ by Visit

The SDQ score for total difficulties score, impact score and the subscale total scores after 3 weeks of double blind treatment and 13 weeks of open-label treatment will be analysed as detailed above for TST.

11.3.5 ESS

Caregiver sleepiness as assessed by the ESS total score and the change from baseline in ESS total score will be summarized by scheduled visit using descriptive statistics. The ESS total score after 3 weeks and 13 weeks of double blind treatment and during open-label treatment will be analysed as detailed above for TST.

11.3.6 PSQI

The global PSQI score and corresponding component scores and changes from baseline will be summarized by scheduled visit using descriptive statistics. The global PSQI score after 3 weeks and 13 weeks of double blind treatment and during open-label treatment will be analysed as detailed above for TST.

11.3.7 WHO-5 Well-being Index

WHO-5 Well-being Index total score and change from baseline in the total score will be summarized by scheduled visit using descriptive statistics. The Well-being Index total score after 3 weeks and 13 weeks of double blind treatment and during open-label treatment will be analysed as detailed above for TST.

11.3.8 Actigraphy by Visit

The shift in time to going to bed will be tabulated by scheduled visit. The categories used will be as detailed for Sleep and Nap Diary Time to bed.

The number and percentage of subjects defined as a responder according to actigraphy will be tabulated for the run-in period. A responder is defined as > 6 hours of continuous sleep and < 0.5 hour sleep latency from light off in 3 out of 5 nights.

11.4 Other Efficacy Variables

11.4.1.1 Quality of Sleep

The quality of sleep as assessed by a Sleep and Nap Diary will be calculated as the mean of the last 14 days prior to each scheduled visit. Quality of sleep will be scored as follows:

Very bad = 1; bad = 2; fair = 3; good = 4; very good = 5; unknown = not scored.

The mean quality of sleep and change from baseline in the mean quality of sleep during the day will be summarized by scheduled visit using descriptive statistics. The change from baseline in the mean quality of sleep at 13 weeks will be analysed as detailed above for TST.

11.4.1.2 Current Alertness

The current alertness as assessed by a Sleep and Nap Diary will be calculated as the mean of the last 14 days prior to each scheduled visit. Current alertness will be scored as follows:

Very tired = 1; tired = 2; quite alert = 3; alert = 4; very alert = 5; unknown = not scored.

The mean current alertness and change from baseline in the mean current alertness during the day will be summarized by scheduled visit using descriptive statistics. The change from baseline in the mean current alertness at 13 weeks will be analysed as detailed above for TST.

11.4.1.3 Feeling on Awakening

The child's feeling on awakening as assessed by a Sleep and Nap Diary will be calculated as the mean of the last 14 days prior to each scheduled visit. Feeling on awakening will be scored as follows:

Very fatigued = 1; fatigued = 2; somewhat refreshed = 3; refreshed = 4; very refreshed = 5; unknown = not scored.

The mean feeling on awakening and change from baseline in the mean feeling on awakening during the day will be summarized by scheduled visit using descriptive statistics. The change from baseline in the mean feeling on awakening at 13 weeks will be analysed as detailed above for TST.

11.4.1.4 Number of Naps

The number of naps during the day as assessed by a Sleep and Nap Diary will be calculated as the mean of the last 14 days prior to each scheduled visit. The mean number of naps during the day and change from baseline in the mean number of naps during the day will be summarized by scheduled visit using descriptive statistics. The change from baseline in the mean number of naps at 13 weeks will be analysed as detailed above for TST.

11.4.1.5 Duration of Naps

The duration of naps during the day as assessed by a Sleep and Nap Diary will be calculated as the mean of the last 14 days prior to each scheduled visit. The mean duration of naps during the day and change from baseline in the mean duration of naps during the day will be summarized by scheduled visit using descriptive statistics. The change from baseline in the mean duration of naps at 13 weeks will be analysed as detailed above for TST.

11.4.2 CSDI

Sleep disturbance as assessed by the CSDI and change from baseline will also be summarized by scheduled visit for each treatment group using descriptive statistics, for each of the individual questions. The change

from baseline in the total CSDI score at 13 weeks for of the individual questions, will be analysed as detailed above for TST.

Individual questions will be scored as follows:

Questions 1, 3, 5 and 6 - 3 or more nights a week = 2; 1 or 2 nights a week = 1; less than once a week = 0;

Questions 2 and 4 - More than 30 minutes = 2; up to 30 minutes = 1; few minutes = 0;

Question 7 - Completely dissatisfied = 1; mostly dissatisfied = 2; neither satisfied nor dissatisfied = 3; mostly satisfied = 4; completely satisfied = 5.

11.5 Missing Efficacy Data

11.5.1 Multiple Imputation

For the primary efficacy variable and the secondary efficacy variables collected using the Sleep and Nap Diary, an analysis will be undertaken to assess the effect of missing data arising on the estimated treatment effects. This will be done using a pattern mixture model where missing data from subjects who are withdrawn is imputed with observations imitating the placebo response [2].

Specifically, using the absolute values for baseline, Week 5 and Week 15, a monotone multiply imputed (1000 imputations) dataset will be initially created. Using this dataset the remaining missing data will then be imputed (1 imputation) using an imputation model based on sequential regression methodology. Starting at Week 5, values for subjects that have missing data will be imputed based on all placebo-treated subjects having a value at that visit. The effect of this is to mimic the expected response as if the withdrawn subjects had been treated with placebo from the point of withdrawal. Next, at Week 15, values for subjects that have missing data will be imputed based on all placebo-treated subjects having a value at that visit. The change from baseline to Week 15 will then be calculated.

These imputed datasets will be analysed separately using ANCOVA with randomised treatment as a factor and baseline as a covariate. The individual results will then be combined using the method of Rubin [3]. The adjusted mean change from baseline (and standard error) in TST after 13 weeks of treatment for each treatment group, the estimated difference (and standard error) between treatments, the associated 95% CI presented and the p-value for the test of null hypothesis that these means are equal will be presented.

Example SAS code for this analysis is given below:

```
* Create monotone dataset;
proc mi data=tst out=mi_mono nimpute=1000 seed=5635245;
  by trtp;
  var week_0 week_3 week_13;
  mcmc impute=monotone;
run;

* Pattern mixture model with placebo-based imputation;
* Impute week 3;
data mi_impl mi_rest1;
  set mi_mono;
```

```
if trtp='Circadin' and lastwk>=3 then output mi_rest1;
else output mi_imp1;
run;

proc mi data=mi_imp1 out=mi_reg_imp1 nimpute=1 seed=8254340;
  class gender disease;
  var week_0 week_3;
  monotone regression;
  by _imputation_;
run;

data midata_2;
  set mi_rest1 mi_reg_imp1;
  by _imputation_;
run;

* Impute week 13;
data mi_imp2 mi_rest2;
  set midata_2;
  if trtp='Circadine' and lastwk=13 then output mi_rest2;
  else output mi_imp2;
run;

proc mi data=mi_imp2 out=mi_reg_imp2 nimpute=1 seed=1066436;
  class gender disease;
  var week_0 week_3 week_13;
  monotone regression;
  by _imputation_;
run;

data tst_mi;
  set mi_rest2 mi_reg_imp2;
  by _imputation_;
  chg=week_13-week_0;
  base=week_0;
run;

* Perform analysis;
proc mixed data=tst_mi;
  class trtp gender disease;
  model chg=trtp base;
  lsmeans trtp/cl diff;
  by _imputation_;
  ods output Diffs=est LSMeans=ls;
run;

* Combine estimates of adjusted means from each imputation;
proc sort data=ls;
  by trtp;
run;

proc mianalyze data=ls;
  by trtp;
  modeleffects estimate;
  stderr stderr;
  ods output ParameterEstimates=milsm;
run;
```

```
* Combine estimates of treatment difference from each imputation;  
proc mianalyze data=est;  
  modeleffects estimate;  
  stderr stderr;  
  ods output ParameterEstimates=midiff;  
run;
```

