  model chg=trtp avisitn base trtp(avisitn) base(avisitn)/ddfm=kr;
  repeated avisitn/subject=subjid type=un;
  lsmeans trtp(avisitn)/diff cl om;
  ods output lsmeans=lsm(where=(avisitn=4)) diffs=diff(where=(avisitn=4));
run;
```

In addition, the effect size will be calculated based on Cohen's d (mean difference between groups/pooled standard deviation) where the mean difference is adjusted for other model factors using MMRM and the pooled standard deviation is evaluated using the model standard errors as follows:

$$sd_{pool} = \sqrt{\left((se_{circ} * se_{circ} * (n_{circ} - 1) * n_{circ}) + (se_{plac} * se_{plac} * (n_{plac} - 1) * n_{plac}) \right) / (n_{circ} + n_{plac} - 2)}$$

where n_{circ} and n_{plac} are the number of subjects with a measurement at Visit 4 (Week 15) and se_{circ} and se_{plac} are the standard errors of the adjusted means in the Circadin and Placebo groups respectively.

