Table 14.2.12.5	WHO-5 Well-Being Index Score Change from Baseline Analysis During the Open Label Phase	FAS Set
Table 14.2.13.1	Actigraphy Shift in Time to Bed by Scheduled Visit	FAS Set
Table 14.2.13.2	Number of Responders as per Actigraphy during the Run-In Period	All Enrolled Set
Table 14.2.14.1	SND Total Sleep Time Change from Baseline at 13 Weeks Double Blind – MI Analysis	All Randomized Set
Table 14.2.14.2	SND Sleep Latency Change from Baseline at 13 Weeks Double Blind – MI Analysis	All Randomized Set
Table 14.2.14.3	SND Duration of Wake Change from Baseline at 13 Weeks Double Blind – MI Analysis	All Randomized Set
Table 14.2.14.4	SND Number of Awakenings Change from Baseline at 13 Weeks Double Blind – MI Analysis	All Randomized Set
Table 14.2.14.5	SND Longest Sleep Duration Change from Baseline at 13 Weeks Double Blind – MI Analysis	All Randomized Set
Table 14.2.14.6	SND Total Sleep Time Change from Baseline at 13 Weeks Double Blind – BOCF Analysis	All Randomized Set
Table 14.2.14.7	SND Sleep Latency Change from Baseline at 13 Weeks Double Blind – BOCF Analysis	All Randomized Set
Table 14.2.14.8	SND Duration of Wake Change from Baseline at 13 Weeks Double Blind – BOCF Analysis	All Randomized Set
Table 14.2.14.9	SND Number of Awakenings Change from Baseline at 13 Weeks Double Blind – BOCF Analysis	All Randomized Set
Table 14.2.14.10	SND Longest Sleep Duration Change from Baseline at 13 Weeks Double Blind – BOCF Analysis	All Randomized Set
Table 14.2.14.11	SND Total Sleep Time Change from Baseline at 13 Weeks Double Blind – MMRM Analysis including Geographic Region as a Factor	FAS Set
Table 14.2.14.12	SND Total Sleep Time Change from Baseline at 13 Weeks Double Blind – MMRM Analysis including Center as a Factor	FAS Set
Table 14.2.14.13	SND Total Sleep Time Change from Baseline at 13 Weeks Double Blind – MMRM Analysis including Age as a Factor	FAS Set
Table 14.2.14.14	SND Total Sleep Time Change from Baseline at 13 Weeks Double Blind – MMRM Analysis including Gender as a Factor	FAS Set

Table Number	Table Title	Population
Table 14.2.14.15	SND Total Sleep Time Change from Baseline at 13 Weeks Double Blind – MMRM Analysis including ADHD as a Factor	FAS Set
Table 14.2.14.16	SND Total Sleep Time Change from Baseline at 13 Weeks Double Blind – MMRM Analysis including Autism Type as a Factor	FAS Set
Table 14.2.14.17	SND Total Sleep Time Change from Baseline at 13 Weeks Double Blind – MMRM Analysis including Epilepsy as a Factor	FAS Set

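### The SAP 11.5.1 example code spells the active-arm label differently at Week 5 and Week 15, so at least one step of the placebo-based imputation would be fitted to both arms pooled

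*SAP*

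**What the plan says.** SAP 11.5.1 describes a pattern-mixture analysis of total sleep time (TST) and the secondary diary outcomes. The text imputes missing values from placebo-treated children at Week 5, and does so again at the next visit: "Next, at Week 15, values for subjects that have missing data will be imputed based on all placebo-treated subjects".

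The example SAS code names these visits by weeks on treatment (`week_3` and `week_13`). It works in two rounds:

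- Before the Week 5 regression, observed active-arm children are set aside with "if trtp='Circadin' and lastwk>=3 then output mi_rest1".
- Before the Week 15 regression, the corresponding line is "if trtp='Circadine' and lastwk=13 then output mi_rest2".
- All other records go into the regression. The Week 15 regression uses "var week_0 week_3 week_13" and runs by imputation number, with no treatment term and no split by arm.
- The two parts are then stacked with "set mi_rest2 mi_reg_imp2".

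Elsewhere the SAP names the arm without a final e, for example "standard errors of the adjusted means in the Circadin and Placebo groups respectively" in 11.1.1. The output goes to Tables 14.2.14.1 to 14.2.14.5; the first is titled "SND Total Sleep Time Change from Baseline at 13 Weeks Double Blind – MI Analysis".

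**The concern.** The two tests use different labels, and `trtp` is not recoded between them. Because the regressions carry no treatment term, the splits are the only part of the code that keeps the fit placebo-only. If a split never matches, every observed active-arm child enters that regression, and missing values in both arms are drawn from a model of the two arms combined.

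If `mi_rest2` is empty, the stacking step still runs, so tables would be produced. The sign of trouble would be a zero record count in the log. If the slip were carried into production, five tables labelled as the missing-data sensitivity analysis would not rest on the assumption the SAP states for them.

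**Working it through.** **Label trace.** SAS pads the shorter string with blanks when comparing, so a final e is a real difference.

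| Stored `trtp` | Week 5 test | Week 15 test | Regression pooled over arms |
|---|---|---|---|
| Circadin | can match | never matches | Week 15 |
| Circadine | never matches | can match | Week 5 |
| any other code | never matches | never matches | both |

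**Inputs from the plan (SAP 6.1 and 6.2).** TST changes 0.72 and 0.27 h, so the Week 15 effect is E15 = 0.45 h; SDs 0.69 and 0.45 h; 120 randomized 1:1. The planned sample size reproduces. The root-mean-square SD is √((0.69² + 0.45²)/2) = 0.582. The normal approximation gives 44 per arm; the t calculation gives 45, with power 95.2% (pooled) or 95.1% (Welch).

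**Assumed, because the documents do not give them.** Dropout by arm to Week 15 (dC, dP) and its timing, the Week 5 effect (E5), the within-arm correlation r of the Week 5 and Week 15 changes, equal SDs at the two visits, and change independent of baseline. The only loss figure is at least 90 of 120 completing Week 28, i.e. up to 1 − 90/120 = 25%.

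**Formulas, with `trtp` stored as 'Circadin'.**

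- Circadin share of observed children: w = (1 − dC)/(2 − dC − dP).
- Intended (placebo-only) slope: r.
- Pooled slope: b = [rV + w(1 − w)·E5·E15]/[V + w(1 − w)·E5²], with V = w·0.69² + (1 − w)·0.45².
- Shift in a placebo child's imputed value: s = w(E15 − b·E5). It is the same for a Circadin child lost before Week 5.
- Shift in the treatment difference, dropout before Week 5: (dC − dP)·s.
- Shift in the treatment difference, dropout after Week 5: (dC − dP)·s + dC(b − r)·E5.

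**No information at Week 5 (E5 = 0, r = 0).** The shift is (dC − dP) × w × 0.45:

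- equal dropout: 0
- 35%/15% (Circadin/placebo): 0.20 × 0.433 × 0.45 = +0.039 h
- 15%/35%: −0.20 × 0.567 × 0.45 = −0.051 h

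**Reference case (dropout before Week 5, E5 = 0.225, r = 0.6).**

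- 25%/25%: w = 0.5, V = 0.339, b = 0.229/0.352 = 0.650, s = 0.5(0.45 − 0.650 × 0.225) = 0.152. Each arm mean rises by 0.25 × 0.152 = 0.038 h (placebo 0.270 to 0.308 h). The difference stays at 0.338 h.
- 35%/15%: s = 0.131; the difference goes from 0.293 to 0.319 h.
- 15%/35%: s = 0.173; the difference goes from 0.383 to 0.348 h.

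**Range for r from 0.4 to 0.8, E5 half of or equal to E15, dropout before or after Week 5.**

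| Dropout, Circadin/placebo | Shift in TST difference |
|---|---|
| equal (25/25 or 15/15) | 0.000 to +0.009 h |
| 35/15 | +0.007 to +0.035 h |
| 15/35 | −0.039 to −0.007 h |

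These are assumed cases, not bounds.

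**Does the direction follow a rule?**

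- With E5 = E15, r = 0.4, dropout after Week 5 and 24%/26% loss: w = 0.507, b = 0.478, s = 0.119. The shift is −0.02 × 0.119 + 0.24 × 0.0775 × 0.45 = +0.006 h, although placebo loses more children.
- With E5 = 1.5 × E15 = 0.675, r = 0.8, dropout before Week 5 and 25%/25%: b = 0.766, s = 0.5(0.45 − 0.766 × 0.675) = −0.034. Both arm means fall by 0.008 h. In the same setting the difference shifts by −0.006 h at 35%/15% and +0.008 h at 15%/35%, the reverse of the table.

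**Standard error.** In a simulation of both versions (60 per arm, 25% missing per arm with no Week 5 value, r = 0.6, Week 5 effect 60% of the Week 15 effect, assumed baseline SD 1.0 h), the standard error of the difference was 0.114 h as intended and 0.121 h with Week 15 pooled.

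**The case against.** The text states the rule correctly, and the block is offered only as example code for a sensitivity analysis. It cannot run exactly as printed: "proc mi data=tst out=mi_mono nimpute=1000 seed=5635245" is run by arm, so a sort is needed before the later steps by imputation number, and `lastwk` is never derived. It also declares gender and disease as class variables that appear in no variable list or model. A programmer must therefore rework it, and harm needs that person to leave this one label alone and miss an empty dataset. The effect is small in any case: 0.039 h is 2.3 minutes, against the 45-minute TST responder threshold in SAP 11.3.1.

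Most of this stands and keeps the point minor. It does not remove it. None of the necessary repairs touches the label, and the code is the SAP's most concrete statement of the method.

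It is also fair that the stored value of `trtp` is nowhere documented. A reader might conclude that the Week 15 line is certainly the wrong one. The SAP's naming makes that likely but does not establish it, so the consequence is stated for each coding.

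**Conclusion.** The inconsistency is certain: no stored value satisfies both tests. It is an error in analysis code, not a questionable choice of method, and it is minor. If carried into production with the arm stored as 'Circadin', the Week 15 step would not be placebo-based, and Tables 14.2.14.1 to 14.2.14.5 would not be the analysis the text describes. Under the stated assumptions, the TST difference moves by 0 to 0.009 h at equal dropout and by up to about 0.04 h either way at 35%/15% or 15%/35%. The size was not worked out for the case where Week 5 is pooled.

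Three stronger readings are not supported:

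- That the slip favours Circadin, or always draws imputed values towards the Circadin mean. Placebo dropouts are imputed from the same pooled model, and the signs depend on dropout by arm, its timing, the Week 5 effect and the correlation.
- That the arm losing more children fixes the sign. The 24%/26% case contradicts it.
- That a direction can be given for sleep latency, wake duration, awakenings or longest sleep. The plan gives no planning values for them.

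The SAP text, the primary MMRM, the per-protocol analysis and BOCF do not use this code and are unaffected.

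**What to change.** Use one treatment label or numeric code, matching the dataset, in both splits. Before the Week 15 regression, confirm that `mi_rest2` holds exactly the Circadin children with `lastwk=13` in every imputation. This is a one-letter edit to the example code and one record count, best made before unblinding. The SAP text and all other analyses stay as they are.

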11.5.2 Baseline Observation Carried Forward

In addition to using the MI method, the effect of missing data will also be assessed using the Baseline Observation Carried Forward (BOCF) method. For the primary efficacy variable and the secondary efficacy variables collected using the Sleep and Nap Diary, the analysis will be repeated to assess the effect of missing data arising on the estimated treatment effects by imputing the missing values with the subject's baseline observation. The analysis will be done using the substantive (ANCOVA) model used in the MI approach.

11.6 Subgroup Analysis

11.6.1 Inclusion of Additional Factors in MMRM Analysis

The effect of treatment in subgroups of interest will be assessed by repeating the analysis of the primary efficacy variable by including the following factors in the model, one at a time.

- Geographic region (US v Europe)
- Center
- Age (2-<6 yrs, 6-<12 yrs, >-12 yrs)
- Gender
- ADHD (Yes, No; identified from the medical history)
- Austim Type
- Epilepsy (Yes, No)
- Prior Anti-Epileptic Treatment
- Prior Anti-Depressant Treatment
- Prior Beta-Blockers Use
- Prior Stimulant Use
- Prior ADHD Treatment
- Prior Clonidine Use

From this model, within each subgroup, the adjusted mean change from baseline (and standard error) in TST after 13 weeks of treatment for each treatment group will be calculated and the associated 95% CI for the change presented. Furthermore for each subgroup, the estimated difference (and standard error) between treatments will be estimated, the associated 95% CI presented and the null hypothesis that these means are equal will be tested.

Example SAS code for this analysis is given below:

```
proc mixed data=tst method=reml;  
  class subjid trtp avisitn geog;  
  model chg=trtp avisitn base geog trtp*geog trtp(avisitn) base(avisitn)  
geog(avisitn) trtp*geog(avisitn)/ddfm=kr;  
  repeated avisitn/subject=subjid type=un;
```

```
lsmeans trtp*geog(avisitn)/diff cl om;  
ods output lsmeans=lsmeans(where=(avisitn=4)) diff=diff(where=(avisitn=4 and  
geog=_geog));  
run;
```

The above analysis will be repeated for CSDI, CGAS and Total SDQ at 13 weeks incorporating the following factors into the model:

- ADHD (Yes, No)
- Epilepsy (Yes, No)
- Prior ADHD Treatment
- Prior Clonidine Use

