12.2 STATISTICAL ANALYSIS PLAN

A Statistical Analysis Plan (SAP) will be written and finalized prior to any lock of the study database. The SAP will provide a detailed description of the statistical methods and expand on the details provided in the protocol. Additional analyses may be added. Tables, listing and figures shells will also be provided.

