For all primary and secondary analyses, a mixed-effect repeated-measures model (MMRM) will be fitted to assess any differences in treatment effects over time. The base models will contain the specified outcome measure after baseline as the dependent variable, with independent variables in the form of the baseline score, the study visit (categorical variable) and treatment allocation. A general covariance structure will be assumed. The global treatment effect estimates will be reported, with 95% CIs and p-values. Further analysis will include interaction between treatment and visit. Interaction p-values will be reported with treatment effect estimates at each visit with 95% CI and p-values.

Exploratory

Sleep variables and sleep disturbance will be assessed by the Sleep and Nap Diary and the CSDI, respectively, at baseline (Week 2) and after 3 and 13 weeks of double-blind treatment (Weeks 5 and 15, respectively) by presenting actual and change from baseline for each treatment group using descriptive statistics (n, mean, SD, median, minimum, and maximum). For this outcome, the mean score at 3 weeks will be compared between treatment groups, adjusting for baseline, and by using an ANCOVA model to test the null hypothesis so that these adjusted mean scores are equal.

The CSDI and Sleep and Nap Diary variables will also be summarized after 13, 26, and 39 weeks of open-label treatment (Weeks 28, 41, and 54) by presenting actual values and change from baseline for each treatment group using descriptive statistics (n, mean, SD, median, minimum, and maximum). CSDI will be also summarized after 91 weeks of open-label treatment and at the end of study visit (Week 108) using descriptive statistics (n, mean, SD, median, minimum, and maximum).

The CGAS and SDQ scores will be summarized at baseline (Week 2), after 3 and 13 weeks of double-blind treatment (Weeks 5 and 15, respectively), and after 13 weeks of open-label treatment (Week 28) by presenting actual values and change from baseline for each treatment group using descriptive statistics (n, mean, SD, median, minimum, and maximum).

The ESS, PSQI and WHO-5 scores (for the parent/caregiver) will be summarized at baseline (Week 2), after 3 and 13 weeks of double-blind treatment (Weeks 5 and 15, respectively), after 13, 26, 39, and 91 weeks of open-label treatment (Weeks 28, 41, 54, and 106, respectively), and at the end of study visit

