12.8.3 Visit Dates

Visit dates will be listed.

13 Interim Analysis

All results will be summarized at the end of the first open-label period (Week 28; Visit 5), and will be submitted in the form of a clinical study report (CSR) to the regulatory authorities for evaluation of approval of the study drug for use in the investigated population. This will constitute the final analysis of data up to that point and no statistical adjustment of significance tests is required.

The data from the second open-label period will be summarized on the completion of the study and reported as an appendix to the CSR.

14 Changes to Planned Methodology

The analysis of total CSDI score at 13 weeks has been moved from an exploratory endpoint to a secondary endpoint to reflect the greater importance being placed on this endpoint at the present time.

15 References

- [1] Kenward, M. G. and Roger, J. H. (1997), Small Sample Inference for Fixed Effects from Restricted Maximum Likelihood, *Biometrics*, 53, 983–997
- [2] Ratitch, B. and O’Kelly, M. (2011), Implementation of Pattern-Mixture Models Using Standard SAS/STAT Procedures, in *Proceedings of PharmaSUG 2011 (Pharmaceutical Industry SAS Users Group)*, SP04, Nashville.
- [3] Rubin, D. B. (1987), *Multiple Imputation for Nonresponse in Surveys*, New York: John Wiley & Sons.

16 Tables, Figures and Listings

Tables and listings will be presented landscape. A font size of 8 and a font of courier new will be used throughout for tables and listings. Tables and listings will be provided as a bookmarked pdf. Figures will be provided as individual files.

The subject population being utilized in the table will be indicated in the table title. Page numbers and dates of production will be included in an appropriate place at the bottom of the output. Listings which support the table will also be detailed in an appropriate place at the bottom of the output.

Tables will only be generated where there is sufficient data to warrant the inclusion of the table.

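### SAP 11.6.1 specifies treatment differences and tests within each subgroup level, but not the Week 15 treatment-by-factor contrast that its own model can already estimate

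*SAP*

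**What the plan says.** SAP 11.6.1 repeats the primary TST model with 13 factors added one at a time. For each level it gives the adjusted mean change per arm and then the comparison: "Furthermore for each subgroup, the estimated difference (and standard error) between treatments will be estimated, the associated 95% CI presented and the null hypothesis" of equal means tested. It continues: "The above analysis will be repeated for CSDI, CGAS and Total SDQ at 13 weeks", with four of the factors.

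The example code fits `trtp*geog` and, on its second line, "geog(avisitn) trtp*geog(avisitn)/ddfm=kr". The Week 15 treatment-by-factor contrast is therefore estimable. However, the code requests only least-squares means and pairwise differences, and it keeps only Visit 4 rows in which both means belong to the same factor level. It has no ESTIMATE, CONTRAST or LSMESTIMATE statement and saves no Type 3 tests.

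The subgroup titles in SAP 16.1 (Tables 14.2.14.11 to 14.2.14.22 and the 14.2.15, 14.2.16 and 14.2.17 series) name only the outcome and the factor, for example "MMRM Analysis including Age as a Factor". Elsewhere, Protocol 12.8.1 plans an interaction result for treatment by visit: "Interaction p-values will be reported with treatment effect estimates at each visit with 95% CI and p-values".

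**The concern.** A subgroup section is read to learn whether the effect differs by region, age, epilepsy and so on. That question is answered by the difference between levels in treatment effect, with its uncertainty. A test of no effect inside each level answers something else. Because levels are smaller than the trial and often unequal, one level can reach significance and another miss it when the true effect is identical.

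The plan sets at least 47 such within-level tests: 23 for TST (ten two-level factors and three age bands, leaving out center and autism type, whose level counts are not given), plus 4 factors x 2 levels x 3 outcomes = 24. These results go into the Week 28 report to regulators. Readers would meet differing p-values and would have to derive the relevant contrast themselves.

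**Working it through.** **Inputs.** SAP 6.1: changes of 0.72 h and 0.27 h (difference 0.45 h), SDs 0.69 and 0.45, 45 per arm. SAP 6.2: 120 randomized 1:1, so 60 per arm if nobody is lost. The documents give no subgroup sizes and no baseline-change correlation (rho), so splits of 50/50, 80/20 and 90/10 and rho of 0, 0.5 and 0.7 are assumptions. All figures are for TST; the documents give no SD for CSDI, CGAS or SDQ.

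**The plan's own figure.** v = 0.69² + 0.45² = 0.6786. Normal approximation: n = (1.960 + 1.645)² x 0.6786 / 0.45² = 43.6, so 44. With the t distribution, power is 94.8% at 44 and 95.2% at 45. The stated 45 per arm reproduces.

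**Formulas under a uniform 0.45 h effect.**
- Adjusted variance: v(1 - rho²), which is 0.6786, 0.5090 and 0.3461.
- Overall z = 0.45 / sqrt(v/n).
- Power in a level with share s: Phi(z·sqrt(s) - 1.96).
- Exactly one of two levels significant: p1(1 - p2) + p2(1 - p1).
- Contrast SE: sqrt(v/n x (1/s + 1/(1 - s))).
- Power for a 0.45 h difference between levels: Phi(0.45/SE - 1.96).

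**Example: 80/20, rho = 0, n = 45.** z = 3.66. Large level: Phi(3.277 - 1.96) = 90.6%. Small level: Phi(1.639 - 1.96) = 37.4%. Exactly one: 0.906 x 0.626 + 0.374 x 0.094 = 60%. Contrast SE = sqrt(0.01508 x 6.25) = 0.307 h; power = Phi(1.466 - 1.96) = 31%.

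**All cases** (each cell 50/50, 80/20, 90/10):

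| rho | n per arm | z | Exactly one level significant, % | Contrast SE, h | Power for 0.45 h, % |
|---|---|---|---|---|---|
| 0 | 45 | 3.66 | 39, 60, 75 | 0.246, 0.307, 0.409 | 45, 31, 20 |
| 0 | 60 | 4.23 | 26, 53, 72 | 0.213, 0.266, 0.354 | 56, 40, 25 |
| 0.5 | 45 | 4.23 | 26, 53, 72 | 0.213, 0.266, 0.354 | 56, 40, 25 |
| 0.5 | 60 | 4.89 | 13, 41, 66 | 0.184, 0.230, 0.307 | 69, 50, 31 |
| 0.7 | 45 | 5.13 | 9, 37, 63 | 0.175, 0.219, 0.292 | 73, 54, 34 |
| 0.7 | 60 | 5.93 | 3, 24.5, 53 | 0.152, 0.190, 0.253 | 84, 66, 43 |

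Rows two and three agree because 45/0.75 = 60. At rho 0 to 0.5 the 95% CI half-widths (1.96 x SE) run from 0.36 h to 0.80 h.

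**Age, assumed equal thirds.** Level power is Phi(z/sqrt(3) - 1.96): 56.2%, 68.5% and 80.5% at z = 3.66, 4.23 and 4.89. Some but not all levels significant, 1 - p³ - (1 - p)³: 74%, 65% and 47%. If one band has no effect and two have 0.45 h, the 2-df joint test has noncentrality 0.045n/v and power of 32%, 41% and 53%.

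**Multiplicity of the added contrasts.** Leaving center out, TST has 12 factors by the text and 11 by the table list; CSDI, CGAS and SDQ add 4 x 3 = 12. Total 23 to 24. Expected false signals: 0.05 x 23 = 1.15 to 0.05 x 24 = 1.20. If independent, the chance of at least one is 1 - 0.95²³ = 69% to 1 - 0.95²⁴ = 71%; the factors overlap, so this is approximate.

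**The case against.** **The shells are missing.** Protocol 12.2 says table shells will be provided, and the SAP code is only an example. A title does not list a table's rows. This stands: the documents support saying that the contrast is not specified, not that it will be left out of the tables.

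**No planned inference is wrong.** A reader might infer that the SAP means to declare subgroup differences by comparing significance across levels, or that the interaction was left out of the model. Neither is supported. The SAP states no such rule, and the interaction terms are in the code. Each level also gets an estimate, SE and CI. For the ten two-level factors the contrast can be approximated as d1 - d2 with SE sqrt(SE1² + SE2²). This lowers the stakes but does not cover age, listed as "Age (2-<6 yrs, 6-<12 yrs, >-12 yrs", or autism type if it has more than two levels. Nor are Type 3 tests a substitute: with both interaction terms fitted they concern the visit average and the change across visits, not Week 15.

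**The contrasts are weak and numerous.** This stands, and it is why the estimate and CI should carry the weight.

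**The size depends on assumptions.** It does. At rho = 0.7 discordance falls to 3-9% at 50/50 and 24-37% at 80/20. The 60-per-arm end assumes no loss. Very uneven factors may give no table at all: "Tables will only be generated where there is sufficient data to warrant the inclusion of the table".

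**The treatment-by-visit commitment does not bind the subgroup section.** Agreed; it only shows that the same kind of result is planned elsewhere. Subgroup analyses are supplementary, as Protocol 12.2 allows: "Additional analyses may be added".

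**Conclusion.** The point holds as a minor reporting gap. SAP 11.6.1 specifies within-level differences, CIs and tests. Its text, example code and table titles do not specify the Week 15 treatment-by-factor contrast that the fitted model supports.

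For TST under a uniform 0.45 h effect, discordant significance is common when levels are uneven: about 24% to 60% at 80/20. It is less of a problem at 50/50 (3% to 39%). These are chances of a misleading pattern, not error rates of any planned test. They rest on assumed splits, assumed correlations of 0 to 0.7 and 45 to 60 per arm, and they do not extend to CSDI, CGAS or SDQ.

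It would be wrong to infer that the trial's main result is at risk. The primary comparison and its sample size are untouched.

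**What to change.** For TST, CSDI, CGAS and total SDQ, add to each subgroup table the Week 15 difference between levels in treatment effect with its 95% CI. For factors with more than two levels, such as age, add a joint F-test at that visit. State that any claim that the effect differs between subgroups rests on this contrast and not on within-level significance. Label these results exploratory and unadjusted for multiplicity. Leave the planned within-level and center analyses as they are.

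Prior Stimulant Use is a listed factor without a listed table in SAP 16.1; a table would have to be added, or its absence explained.

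**Cost.** One SAP paragraph, an extra row per existing table, and one ESTIMATE or LSMESTIMATE statement per factor and outcome. Model, sample size, alpha and data collection do not change.

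**Downsides to state.** Power for a 0.45 h difference between levels is about 20% to 69% at correlations of 0 to 0.5, so most contrasts will be inconclusive. About 1.2 false signals are expected over 23 to 24 contrasts. Discordant within-level p-values will still appear; the contrast only lets a reader interpret them.
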